14.2.4.1.2 When index nodal lesions are in complete response

When there is a Complete Response for index nodal lesions (i.e. complete normalization of all index nodal lesions as defined in [Section 14.2.4.2](#): all index lesion ≤ 15 mm in long axis), the SPD for these index nodal lesions may not be equal to zero and therefore a calculation of a SPD for all index lesions may be misleading. Therefore, by default, a specific response for extranodal index lesions needs to be evaluated, based on the SPD calculation restricted to all index extranodal lesions only (see [Table 14-8](#)).

Table 14-8 Radiological response criteria for index extranodal lesions in case of CR in index nodal lesions

Response Criteria ¹	Evaluation of index extranodal lesions
Complete Response (CR)	Complete disappearance of all index extranodal lesions
Partial Response (PR)	At least 50% decrease from Screening in the SPD restricted to all index extranodal lesions
Stable Disease (SD)	Failure to attain the criteria needed for CR or PR and failure to fulfill the criteria for PD
Progressive Disease (PD)	At least a 50% increase from nadir ² in the SPD restricted to all index extranodal lesions

¹ At each assessment, response will be first assessed for meeting CR status. If CR status is not met, response will be assessed for PD status, then PR status and SD status.

² Nadir is defined as the smallest sum of the product of the diameters restricted to all index extranodal lesions recorded so far, at or after Screening.

The algorithm for evaluating the response integrating index extranodal lesions and the SPD calculated on all index lesions (where appropriate) provides an overall response for index lesions.

14.2.4.1.3 Evaluation of response for all index lesions

The evaluation of response for all index lesions is based on the combination of the response for index nodal lesions (CR or non-CR), the response for index extranodal and the status based on the SPD calculated on all index lesions (nodal and extranodal), as described in [Table 14-9](#).

Table 14-9 Radiological response for index lesions

Response for index nodal lesions ¹	Response for index extranodal lesions ¹	Status based on SPD calculation for all index lesions	Response for index lesions
CR	CR	Not calculated	CR
CR	SD/ PR	Not calculated	PR
CR	PD	PD	PD
CR	PD	PR	PR
CR	PD	SD	SD
Non-CR	Not evaluated	PD	PD
Non-CR	Not evaluated	PR	PR
Non-CR	Not evaluated	SD	SD

¹ If no index nodal lesions are present at Screening, then index lesions response is equal to the index extranodal lesions response. A similar rule applied if no index extranodal lesions are present at Screening, then index lesions response is equal to the index nodal lesions response.

In case of missing measurements of any of the index lesions, the radiological response for index lesions at that assessment will be “Unknown (UNK)”, unless progression was seen.

All lesions must have been measured with the same method as the one used at Screening, otherwise the radiological response for index lesions at that assessment will be “Unknown (UNK)”.

14.2.4.1.4 Evaluation of non-index lesions (including nodal, splenic and/or hepatic nodules and other extranodal lesions)

At each reassessment, a non-index lesion (or a group of non-index lesions) will be given one of the following designations:

- Normalization (non-index nodal lesion has regressed to normal size; non-index extranodal lesion is no longer present). Normalization of non-index nodal lesions should be determined based on their size at Screening.
- Improved, stable or worsened, but without unequivocal evidence of disease progression (non-index lesion is present but there is not sufficient worsening to declare PD based on the existing non-index lesions).
- Unequivocal evidence of disease progression (worsening of existing non-index lesions is sufficient to declare PD).
- Not assessed.

Then, this status for each non-index lesion (or group of non-index lesions) will lead to a global response for non-index lesions ([Table 14-10](#)):

Table 14-10 Response criteria for non-index lesions (nodal, splenic and/or hepatic nodules and other extranodal lesions)

Response Criteria	Evaluation of non-index lesions
Complete Response (CR)	Complete normalization of all non-index nodal and extranodal lesions: Radiological regression to normal size of all lymph nodes and complete disappearance of all extranodal (including splenic and/or hepatic nodules) lesions
Stable Disease (SD)	Failure to attain the criteria needed for CR and failure to fulfill the criteria for PD
Progressive Disease (PD)	Unequivocal disease progression of any existing non-index lesions (nodal or extranodal)

In case of a missing status of any of the non-index lesions, the radiological response for non-index lesions at that assessment will be “Unknown (UNK)”, unless progression was seen.

All lesions must have been measured with the same method as the one used at Screening, otherwise the radiological response for non-index lesions at that assessment will be “Unknown (UNK)”.

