14.2.2.1 Measurable Nodal and extranodal lesions

A lesion will be called **measurable** if it can be measured accurately in 2 perpendicular dimensions and:

- For nodal lesion, if the long axis is > 15 mm, regardless of the length of the short axis,
- For extranodal lesion, if the long and short axes are ≥ 10 mm.

Patients should have at least one measurable nodal lesion greater than 20 mm in the long axis.

In cases where the patient has no measurable nodal lesions greater than 20 mm in the long axis at Screening, then the patient must have at least one measurable extranodal lesion.

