14.2.2.3 Criteria for normalization of lesions

The normalization of lesions is defined as follow:

- A measurable nodal lesion must become ≤ 15 mm in long axis to be considered normalized.
- A non-measurable nodal lesion must decrease to ≤ 10 mm in the short axis and be ≤ 15 mm in long axis to be considered normalized.
- An extranodal lesion must disappear completely (assigned a size of 0 mm x 0 mm) to be considered normalized.

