14.2.4 Evaluation of Radiological Response

For the sake of simplicity, complete remission and complete response will both be referred to as complete response.

Definitions of Response for Lymphoma patients are listed in [Table 14-6](#). To evaluate disease response to treatment, all index and non-index lesions will be followed and assessed throughout the study. At each assessment, response is evaluated separately for the **index lesions** ([Table 14-9](#)) and **non-index lesions** ([Table 14-8](#)) identified at Screening, then a combined overall radiological response is determined ([Table 14-11](#)).

Table 14-6 Response Definition for Lymphoma

Response	Definition	Nodal Masses	Spleen. Liver	Bone Marrow
CR	Disappearance of all evidence of disease	a FDG-avid or PET positive prior to therapy; mass of any size permitted if PET negative b Variably FDG-avid or PET negative; regression to normal size on CT	Not palpable, nodules disappeared	Infiltrate cleared on repeat biopsy; if indeterminate by morphology, immunohistochemistry should be negative
PR	Regression of measurable disease and no new sites	≥ 50% decrease in SPD of up to 6 largest dominant masses; no increase in size of other nodes a FDG-avid or PET positive prior to therapy; one or more PET positive at previously involved site b Variably FDG-avid or PET negative; regression on CT	≥ 50% decrease in SPD of nodules (for single nodule in greatest transverse diameter); no increase in size of liver or spleen	Irrelevant if positive prior to therapy; cell type should be specified
SD	Failure to attain CR/PR or PD	a FDG-avid or PET positive prior to therapy; PET positive at prior sites of disease and no new sites on CT or PET b Variably FDG-avid or PET negative; no change in size of previous lesions on CT		
Relapsed disease or PD	Any new lesion or increase by ≥ 50% of previously involved sites from nadir	Appearance of a new lesion(s) > 1.5 cm in any axis, ≥50% increase in SPD of more than one node, or ≥ 50% increase in longest diameter of a previously identified node > 1 cm in short axis Lesions PET positive if FDG-avid lymphoma or PET positive prior to therapy	> 50% increase from nadir in the SPD of any previous lesions	New or recurrent involvement

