14.2.4.1 Evaluation of Index Lesions (nodal and extranodal)

14.2.4.1.1 When index nodal lesions are not in complete response

The response for index lesions is evaluated by calculating the Sum of the Products of Diameters (SPD) of all index lesions (see [Table 14-7](#)), except when there is a Complete Response for index nodal lesions (i.e. complete normalization of all index nodal lesions) (see [Section 14.2.4.1.2](#)).

Table 14-7 Radiological status based on SPD calculation for all index lesions

Response Criteria ¹	Evaluation of index lesions
Complete Response (CR)	See Table 14-9 below (not based on SPD calculation for all index lesions)
Partial Response (PR)	At least 50% decrease from Screening in the SPD of all index lesions
Stable Disease (SD)	Failure to attain the criteria needed for CR or PR and failure to fulfill the criteria for PD
Progressive Disease (PD)	At least a 50% increase from nadir ² in the SPD of all index lesions

¹ At each assessment (if the index nodal lesions are not in CR status), the response status based on SPD calculation will be first assessed for meeting PD status criteria, then PR status and SD status.

² Nadir is defined as the smallest sum of the product of the diameters of all index lesions recorded so far, at or after Screening.

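### Row 2 of protocol Table 14-9 scores nodal CR with merely stable extranodal lymphoma as PR without a total SPD check, so a patient with unchanged or larger index tumor burden can count as a responder.

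*Protocol*

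**What the plan says.** - **Table 14-9, row 2 (protocol 14.2.4.1.3):** "CR SD/ PR Not calculated PR". The columns are index nodes, index extranodal lesions, status from total SPD, and the resulting index response.
- **Nodal CR (protocol 14.2.2.3):** "A measurable nodal lesion must become ≤ 15 mm in long axis to be considered normalized". There is no condition on the short axis. A node is measurable at baseline on this rule (14.2.2.1): "For nodal lesion, if the long axis is > 15 mm, regardless of the length of the short axis".
- **Extranodal SD (Table 14-8):** "Failure to attain the criteria needed for CR or PR and failure to fulfill the criteria for PD", where PD is "At least a 50% increase from nadir" in the extranodal SPD.
- **PR by total SPD (Table 14-7):** "At least 50% decrease from Screening in the SPD of all index lesions". Section 14.2.4.1.1 confines this table to patients whose index nodes are not in CR.
- **Reason for leaving total SPD out (14.2.4.1.2):** normalized nodes keep a non-zero SPD, so a total that includes them could mislead.
- **Carry-through:** under Table 14-11 an index PR becomes an overall radiological PR if non-index lesions are CR or SD and there is no new lesion. Section 14.2.4.2.4 then takes any non-CR radiological response as the disease response.

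**The concern.** A partial response should mean that measurable disease has shrunk. Row 2 instead lets a marginal change in a small node turn stable, or even growing, extranodal disease into PR. It disagrees with three other parts of the same appendix:

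1. **Table 14-6** asks for at least a 50% SPD fall in splenic and hepatic nodules for PR. Section 14.2.1.1.1 classes spleen and liver lesions as extranodal. Nodal CR with unchanged liver nodules therefore fails PR in Table 14-6 but is PR in row 2.
2. **Table 14-9, footnote 1** equates the index response with the extranodal response when there are no index nodes at Screening. Extranodal SD is then SD. Adding one 16 mm node that shrinks by 1 mm turns the same extranodal course into PR.
3. **Table 14-9, rows 3 to 5** (nodal CR, extranodal PD) do use total SPD while the nodes are in CR.

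At stake are the key secondary overall response rate for lymphoma (protocol 10.5.1, SAP 6.2) and the set of responders for whom duration of response is defined (protocol 10.5.2). B-cell lymphoma and ALCL are two of the six groups listed in SAP 10.1.

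**Working it through.** The documents state no tumor-burden figure for this rule, so there is none to reproduce. The lesion sizes below are illustrative assumptions that respect the protocol's measurability limits. Screening is taken as the nadir, with no new lesion and non-index lesions CR or SD.

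**Example.** Baseline: node 16 x 12 = 192 mm², mass 60 x 50 = 3000 mm², total 3192. Follow-up node: 15 x 12 = 180, which is nodal CR.

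| Mass at follow-up | Total SPD | Change in total | Extranodal status | Table 14-9 |
|---|---|---|---|---|
| 3000 (unchanged) | 3180 | 3180/3192 - 1 = -0.4% | SD | PR (row 2) |
| 4470 (+49%) | 4650 | 4650/3192 - 1 = +45.7% | SD | PR (row 2) |
| 4500 (+50%) | 4680 | 4680/3192 - 1 = +46.6% | PD | SD (row 5) |

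The last two lines differ by 30 mm², under 1% of baseline, yet the category drops from PR to SD.

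**General limit.** Let s be the nodal share of baseline SPD, f the nodal SPD ratio and e the extranodal SPD ratio.

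Change in total = s·f + (1 - s)·e - 1

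Under row 2 with extranodal SD, e < 1.50. If nodal SPD does not grow (f ≤ 1), the total is bounded just under +50%. With s = 0.01 and e just under 1.50, the change is +48.7% for f = 0.25 and +49.4% for f = 0.94. If a short axis grows, the bound fails: node 16 x 8 to 15 x 15 with extranodal 10 x 10 at +49% gives 128 + 100 = 228 to 225 + 149 = 374, which is +64%, still PR by row 2.

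**When a row 2 PR is genuine.** Three nodes 40 x 30 to 15 x 10 with extranodal 30 x 30 unchanged: 3600 + 900 = 4500 to 450 + 900 = 1350, which is -70%. Counting normalized nodes as zero, a 50% fall needs (1 - s)·e ≤ 0.5, so s ≥ 1 - 0.5/e. That is 50% nodal share at e = 1.00 and 66% at e = 1.49.

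**Effect on the response rate.** SAP 10.4.1 expects 6 B-cell lymphoma and 6 ALCL patients. One reclassified patient moves a lymphoma response rate by 1/12 = 8.3 points.

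**The case against.** The best defence is that the row is deliberate. Table 14-7 is expressly limited to nodes not in CR, so row 2 does not formally contradict it, and 14.2.4.1.2 explains why total SPD is set aside. Both points stand. But the explanation guards against understating a response because normal nodes still have size. It gives no ground for PR when extranodal disease has not shrunk, and rows 3 to 5 use total SPD regardless.

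A reader might also draw stronger conclusions that the documents do not support:

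- **That Table 14-6 sets a total SPD threshold.** Its criterion "50% decrease in SPD of up to 6 largest dominant masses" stands in the nodal column. The direct conflict is with the spleen and liver column.
- **That about 46% is the ceiling.** That figure belongs to the example's lesion sizes. The limit is just under 50% if nodal SPD does not grow.
- **That one week-8 PR of this kind counts in the primary endpoint.** Protocol 10.4 read alone attaches no duration to PR. However, Appendix Q and SAP 10.1 assess clinical benefit at 16 weeks, and under SAP 6.1 SD at or after week 16 counts just as PR does. Table 7-1, footnote 7, also schedules a confirmation at least 4 weeks later for lymphoma PR. Confirmation does not cure row 2, because the same stable picture is scored PR again.
- **That each patient moves the response rate by 16.7 points (1 of 6).** Protocol 10.5.1 gives only the whole-study rate when groups are below 10. SAP 6.2 summarizes cohorts separately only from 10 subjects and otherwise reports lymphoma as a class.
- **That everyone admitted on extranodal disease is exposed.** Section 14.2.2.1 provides for this entry route: "In cases where the patient has no measurable nodal lesions greater than 20 mm in the long axis at Screening". Those with no index node fall under footnote 1 and stay SD. Exposure needs a small index node beside dominant extranodal disease, and the documents do not say how common that is.

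**Conclusion.** The point holds. Row 2 can score PR for a lymphoma patient whose total index SPD is unchanged, or up to just under 50% larger when nodal SPD does not grow, and it is inconsistent with Table 14-6, footnote 1 and rows 3 to 5. Not every row 2 PR is false, since predominantly nodal disease can show a true fall of 50% or more.

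The consequence is limited to the lymphoma response rate and to which patients enter duration of response. SAP section 2 makes both descriptive, and SAP 2.1 only lists duration of response if responses are few. The size is about 8.3 points per affected patient, assuming the two lymphoma groups together reach the expected 12. How many patients would be affected cannot be derived from the documents. The primary clinical benefit rate is essentially unaffected.

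**What to change.** Split row 2 of Table 14-9:

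- Nodal CR with extranodal PR: PR, as now.
- Nodal CR with extranodal SD: PR only if the SPD of all index lesions is at least 50% below Screening, otherwise SD.

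State one convention for normalized nodes, actual size or zero, and use it in every nodal-CR row that relies on total SPD, including rows 3 to 5. Mixing the two would keep a jump at +50%. For example, take a node 40 x 25 to 15 x 13 (1000 to 195) with extranodal baseline 400. At +49% with the node as zero, 596/1400 is -57%, PR. At +50% with the node at actual size, 795/1400 is -43%, SD. Under a single convention both are PR (zero: 596 and 600 of 1400) or both SD (actual: 791 and 795 of 1400). Actual size leaves rows 3 to 5 as they are. Zero answers the worry in 14.2.4.1.2 but changes the total those rows use, so their categories would need rechecking.

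The cost is one split row, a stated convention and the matching derivation. Section 14.2.3.1.2 already requires index lesion sizes to be entered throughout the study, so no new data are needed. The downside is that a few PRs become SD and the lymphoma response rate may be slightly lower.

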14.2.4.2 New lesions

The appearance of

- any new nodal lesion >15 mm in any axis. New nodal lesion is defined by:
 - either a previously normal lymph node becoming > 15 mm in any axis,
 - or a previously identified abnormal lymph node showing an increase of at least 50% in the long axis,
 - as assessed by investigator

OR

- any discrete extranodal (including splenic and/or hepatic nodules) lesions reliably appearing on CT scan or MRI after Screening.

is always considered as Progressive Disease (PD) and has to be recorded as a new lesion in the appropriate module of the eCRF. Determination of new lymphoma involvement in organs other than lymph nodes or liver or spleen should be confirmed histologically and the site must document that in a comment to the corresponding eCRF.

14.2.4.2.1 Overall radiological response

Overall radiological response is calculated as shown in [Table 14-11](#).

Table 14-11 Overall radiological response at each assessment

Index lesions	Non-index lesions ¹	New lesions	Overall radiological response
CR	CR	No	CR
CR	SD	No	PR
PR	CR or SD	No	PR
SD	CR or SD	No	SD
PD	Any	Yes or No	PD
Any	PD	Yes or No	PD
Any	Any	Yes	PD

Index lesions	Non-index lesions ¹	New lesions	Overall radiological response
¹ If no non-index lesions are present at Screening, then this column is not used in evaluating overall radiological response.			

If the evaluation of any of the index or non-index lesions identified at Screening could not be made during follow-up or if the index or non-index response is “Unknown (UNK)”, the overall response status at that assessment must be “Unknown (UNK)” unless progression or a new lesion was seen.

14.2.4.2.2 Evaluation of overall disease response

The evaluation of overall disease response at each assessment is a composite of the individual radiological responses (index and non-index lesions, new lesions), laboratory test (bone marrow) and clinical responses (lymphoma related clinical symptoms).

14.2.4.2.3 Bone marrow re-assessment at time of radiological CR

In order to confirm a Complete disease response (CR), bone marrow biopsy or aspirate may be required when a radiological CR has been achieved. Details are provided in the Study Protocol. The infiltrate of lymphoma in bone marrow must have cleared on repeat bone marrow biopsy or aspirate. Patients who achieve a CR by other criteria but who have persistent morphologic positive or inconclusive bone marrow involvement will be considered partial responders. New or recurrent bone marrow involvement anytime during the follow up will be considered PD. Bone marrow biopsy or aspirate will be performed after the first assessment of CR or when clinically indicated.

The biopsy sample of bone marrow must be adequate (with a goal of > 20 mm unilateral core). If the sample is indeterminate by morphology, it should be negative by immunohistochemistry.

14.2.4.2.4 Overall disease response

If a patient has an overall radiological response of CR then this response must be confirmed by bone marrow biopsy or aspirate (if required as per the Study Protocol), presence of normal liver and spleen size, and evaluation of lymphoma related B-symptoms. The patient's overall response will be calculated as follows:

A patient will be deemed to have overall disease response of CR if bone marrow biopsy or aspirate becomes negative for tumor involvement (if the bone marrow was involved by lymphoma at Screening) and the liver and spleen are normal in size and there are no lymphoma related B-symptoms in addition to radiological CR.

If assessments of any of the following: lymphomatous infiltration of bone marrow (If required as per the Study Protocol), or evaluation of B-symptoms is not done, unknown or indeterminate or B-symptoms are still present when the overall radiological response is assessed as CR or the liver or spleen are enlarged, then the overall disease response will be assessed as PR until evaluation of these factors have shown normalized results and recorded on the corresponding eCRF.

For patients whose radiological response is anything other than CR, assessment of bone marrow, liver, spleen and B-symptoms will not be required in evaluating overall response and

overall disease response is the same as radiological response. However any new or recurrent bone marrow involvement at any time during follow-up will be considered PD.

Of note, appearance of B-symptoms or enlarged spleen or liver will not in themselves constitute documentation of progression. They are however expected to be associated with progressive disease. Every effort should be made to document that evidence radiologically and report the corresponding tumor assessments. Such tumor assessments are expected to be performed within 2 months of appearance of B-symptoms or enlarged spleen or liver.

14.3 Appendix C: Ann Arbor staging classification

Stage	Area of involvement
I	Single lymph node group
II	Multiple lymph node groups on the same side of the diaphragm
III	Multiple lymph node groups on both sides of the diaphragm
IV	Multiple extranodal sites or lymph nodes and extranodal disease
X	Bulk disease > 10 cm
E	Extranodal extension or single isolated site of extranodal disease
Class A are patients who experience no B symptoms	
Class B are patients experience unexplained fever of $\geq 38^{\circ}\text{C}$; unexplained, recurrent drenching night sweats; or unexplained loss of $>10\%$ body weight within the previous 6 months	
¹ Cotswolds modification of Ann Arbor staging system adapted from 2007 NCCI guidelines for non-Hodgkin's lymphoma	

14.4 Appendix D: Rai Staging System^a

Stage	Area of involvement	Risk Status
0	Lymphocytosis, lymphocytes in blood $>15 \times 10^9/\text{L}$ and $>40\%$ lymphocytes in bone marrow	Low
I	Stage 0 with enlarged node(s)	Intermediate
II	Stage 0-1 with splenomegaly, hepatomegaly, or both	Intermediate
III ^b	Stage 0-II with hemoglobin $< 11.0 \text{ g/dL}$ or hematocrit $<33\%$	High
IV ^b	Stage 0-III with platelets $<100 \times 10^9/\text{L}$	High

^a Research originally published in Blood. Rai KR et al. Clinical staging of chronic lymphocytic leukemia. Blood 1975;46(2):219-234. (c) The American Society of Hematology

^b Immune-mediated cytopenias are not the basis for these stage definitions.

14.5 Appendix E: Criteria for Response assessment in Acute Myeloid Leukemia (based on IWG and Cheson)

Disease assessments will be based on standardized response criteria as defined by the International Working Group (IWG) for AML (Cheson et al 2003).

Response classification in AML at a given evaluation time (Cheson 2003)	
Response category	Definition [#]
Complete remission (CR)	
Bone marrow $< 5\%$ blasts no blasts with Auer rods
 
Peripheral blood neutrophils $\geq 1.0 \times 10^9/\text{L}$ platelets $\geq 100 \times 10^9/\text{L}$ $\leq 1\%$ blasts No evidence of extramedullary disease (such as CNS or soft tissue involvement). Transfusion independent (see Section 7.2.1.4.5).
 
In case all criteria for CR apply and the patient receives platelet and/or neutrophil transfusions, the patient will be assessed as CRi.

Response classification in AML at a given evaluation time (Cheson 2003)	
Response category	Definition [#]
Complete remission with incomplete blood count recovery (CRI)	
Bone marrow < 5% blasts no blasts with Auer rods
 
Peripheral blood neutrophils < $1.0 \times 10^9/L$ and/or platelets < $100 \times 10^9/L$ ≤ 1% blasts No evidence of extramedullary disease (such as CNS or soft tissue involvement). Transfusion-independent (see Section 7.2.1.4.5). Exception: Platelet and neutrophil transfusions are allowed.

Partial Remission (PR)	
Bone marrow 50% or greater decrease (absolute range 5-25% blasts) < 5% of blasts contain Auer rods
 
Peripheral blood neutrophils < $1.0 \times 10^9/L$ and/or platelets < $100 \times 10^9/L$ No evidence of extramedullary disease (such as CNS or soft tissue involvement).

Treatment failure	Treatment failure includes those patients for whom treatment has failed to achieve PR, CRI or CR throughout the treatment.
Relapse from CR or CRI*	Only in patients with a CR or CRI: Reappearance of blasts in peripheral blood (> 1%) OR ≥ 5% blasts in bone marrow OR (Re-)appearance of extramedullary disease
No response	In case a patient does not achieve CR, CRI, PR or relapse for an individual response assessment.
Unknown	In case the response assessment was not done, the baseline assessment was not done, the assessment was incomplete or was not done within the respective time frame.

[#] If not defined otherwise, all of the criteria apply.
 * Cheson et al (2003) does not specify relapse after PR but this may be considered in Phase I or II protocols.

Table 14-12 Exploratory AML response categories according to IWG

Response category	Definition
Cytogenetic complete remission (CRc)	All criteria for CR plus no cytogenetic abnormalities
Molecular complete remission (CRm)	All criteria for CRc plus no leukemic cells by RQ-PCR assay

14.6 Appendix F: Criteria for Response assessment in Acute Lymphoblastic Leukemia (based on NCCN Guidelines Version 1.2013)

Response classification in ALL for Blood and Bone Marrow at a given evaluation time	
Response category	Definition [#]
Complete remission (CR)	No circulating blasts or extramedullary disease (such as lymphadenopathy, splenomegaly, skin/gum infiltration, testicular mass, CNS or soft tissue involvement) Trilineage hematopoiesis (TLH) and < 5% blasts neutrophils $\geq 1.0 \times 10^9/L$ platelets $\geq 100 \times 10^9/L$ No recurrence for 4 weeks

Response classification in ALL for Blood and Bone Marrow at a given evaluation time	
Response category	Definition[#]
Complete remission with incomplete blood count recovery (CRi)	Peripheral blood Recovery of platelets but $< 100 \times 10^9/L$ or neutrophils is $< 1.0 \times 10^9/L$.
Progressive Disease (PD)	Increase of at least 25% in the absolute number of circulating or bone marrow blasts or development of extramedullary disease.
Treatment failure	Treatment failure includes those patients for whom treatment has failed to achieve a CR at the end of treatment
Relapse from CR or CRi*	Only in patients with a CR or CRi: Reappearance of blasts in peripheral blood ($> 1\%$) OR $\geq 5\%$ blasts in bone marrow OR (Re-)appearance of extramedullary disease
No response	In case a patient does not achieve CR, CRi, PR or relapse for an individual response assessment.
Unknown	In case the response assessment was not done, the baseline assessment was not done, the assessment was incomplete or was not done within the respective time frame.

[#] If not defined otherwise, all of the criteria apply.

14.7 Appendix G: Criteria for Response assessment in Chronic Myelogenous Leukemia (based on NCCN Guidelines Version 4. 2013)

Response classification in CML for hematologic, cytogenetic, and molecular evaluation at a given evaluation time	
Response category	Definition[#]
Complete hematologic response (CR) ¹	Complete normalization of peripheral blood counts with leukocyte count $< 10 \times 10^9/L$ platelets $< 450 \times 10^9/L$ No immature cells such as myelocytes, promyelocytes, or blasts in peripheral blood No signs and symptoms of disease with disappearance of splenomegaly
Cytogenetic response ^{2,3}	Complete No Ph-positive metaphases Partial $1\% - 35\%$ Ph-positive metaphases Major $0\% - 35\%$ Ph-positive metaphases (complete + partial) Minor $> 35\%$ Ph-positive metaphases
Molecular response ^{4,5}	Complete No detectable BCR-ABL mRNA by QPCR using an assay with a sensitivity of at least 4.5 logs below standardized baseline. Major ≥ 3 log reduction in international scale of BCR-ABL mRNA
Treatment failure	Treatment failure includes those patients for whom treatment has failed to achieve a complete hematologic response (CR) throughout treatment.
No response	In case a patient does not achieve CR, PR or relapse for an individual response assessment.
Unknown	In case the response assessment was not done, the baseline assessment was not done, the assessment was incomplete or was not done within the respective time frame

Response classification in CML for hematologic, cytogenetic, and molecular evaluation at a given evaluation time	
Response category	Definition[#]
